16.3 Relationship to Study Medical Product

An investigator, who is a qualified physician, should assess the relationship to the study medical device and the substrate, based on all information available at the time of assessment.

The following definitions should be used:

- **Not Related:**

1. The event is clearly related to other factors such as the patient's clinical state, therapeutic interventions or concomitant drugs.
2. There is a highly likely alternative explanation.

- **Related:**

1. The event AE is reasonably associated with the use of the investigational product (device or substrate).

16.4 Adverse Event Severity

- **Mild Adverse Events**

A mild adverse event is one that the symptoms are barely noticeable to the patient. It does not influence performance, require drug treatment or prevent the patient from carrying on with normal life activities.

- **Moderate Adverse Events**

A moderate adverse event is one that the symptoms make the patient uncomfortable and causes some impairment to normal life activities. Treatment for symptom(s) may be required.

- **Severe Adverse Events**

A severe adverse event is one that the symptoms cause severe discomforts to the patient and severely limits the patient's normal daily activities. Treatment for symptom(s) is given.

Note: Serious and severe are not synonymous. A serious adverse event must fulfill the requirements listed in the definition above.

16.5 Adverse Event Reporting

The investigator should report all adverse events in the case report form. The investigator is responsible for the appropriate medical management of all adverse events.

Exalenz Bioscience Ltd.	Last update on: Nov 21, 2016
Study Title: Clinical Study of the BreathID[®] MCS System to train the algorithm for the ¹³C-Methacetin Breath Test (MBT) in assessment of Portal Hypertension in Patients with Compensated Liver Cirrhosis	Protocol No.: CSPH-EX-0414 Version: 1.5
Document N^o: CSD00076	Page 50 of 72

The investigator must report any serious adverse event to the sponsor immediately, within 24 hours of awareness, via email. Full details of the event, severity, outcome (if available) and an assessment of the relationship to the study investigational product must be provided in the report.

All SAEs must be followed up until resolution or stabilization by submission of updated reports. Follow-up SAE reports will be reported according to the same timelines as initial reports, as soon as new significant information becomes available.

All SAEs that fulfill UADE or SUSAR definitions will be reported to the relevant authorities by expedited means.

Notification of the IECs/IRBs and regulatory authorities

Notification to the IECs/IRBs about all relevant events (e.g. SAEs, UADEs, SUSARs) will be performed by the sponsor and/or by the investigator according to all applicable regulations.

The processing and reporting of all relevant events to the regulatory authorities will be done by the sponsor according to all applicable regulations.

If unexpected safety issues are identified, specific amendments will be implemented.

16.6 Study-Specific Exceptions

Disease complications as a result of disease progression is expected and it is not necessary to report them as SUSARs, but they should be reported in the follow-up section of the case report form (CRF).

The following situations and non-fatal toxicities that fulfill the definition of an SAE are excluded from expedited notification on an SAE form, but should be reported in the follow-up section of the CRF form:

- Elevation of bilirubin
- Elevation liver enzymes
- Nausea, vomiting , diarrhea
- Bleeding following line insertion

Although these events are anticipated to occur as part of the disease process, they will be collected and periodically analyzed to assess whether they are occurring at a higher rate than would be expected in this population. If certain events occur at a higher rate than expected for a given stage or severity of the disease, then the adverse event analysis will be reported under

Exalenz Bioscience Ltd.	Last update on: Nov 21, 2016
Study Title: Clinical Study of the BreathID[®] MCS System to train the algorithm for the ¹³C-Methacetin Breath Test (MBT) in assessment of Portal Hypertension in Patients with Compensated Liver Cirrhosis	Protocol No.: CSPH-EX-0414 Version: 1.5
Document N^o: CSD00076	Page 51 of 72

expedited reporting requirements. (FDA Guidance: Safety Reporting Requirements for INDs and BA/BE Studies. <http://www.fda.gov/downloads/Drugs/.../Guidances/UCM227351.pdf>)

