11.5 Safety Termination of Subjects or Study

1. Withdrawal of patients from the study if they have a CTCAE Grade 3 or higher regardless of whether the event is attributed to the drug unless it is caused by an accident that could not reasonably be attributable to the drug (CTCAE: Common Terminology Criteria for Adverse Events Version 4.0).
2. Discontinuance of study, if ≥ 2 patients on Methacetin develop the same CTCAE Grade 3 event or 1 patient develops a CTCAE Grade 4 or higher event due to the breath test.

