Major complications have been limited to local injury at the puncture site, including leakage, hematoma and rarely an arteriovenous fistula or Horner syndrome. Ultrasonographic guidance reduces the risk of procedural complications. Passage of the catheter through the right atrium might cause supraventricular dysrhythmias that are self-limited in more than 90% of cases. Although coagulation disorders are common in patients with cirrhosis, only severe thrombocytopenia (platelets <20,000/mm³) calls for platelet transfusion. The procedure entails very little discomfort, is carried out under moderate conscious sedation that does not influence HVPG measurement. The procedure’s acceptability is comparable to that of upper gastrointestinal endoscopy.

Complications of the HVPG measurement will be reported as anticipated Adverse Events. The test procedure in this protocol is the MBT. The HVPG should be performed for clinical cause according to local standards of care; the HVPG will not be performed for the purpose of enrolling a patient under this protocol. For the purpose of the study, in US centers the HVPGs is considered an investigational procedure since HVPG is not used as common practice in the US.

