Document N^o: CSD00076	Page 72 of 72

actual measurement. CO₂ production with ¹³C may be visible within a few minutes in cases with relatively functional livers.

Note: In rare cases the administration of fluids may cause vomiting. If this happens the test should be aborted and repeated the next day. The expected adverse event should be reported in the appropriate CRF section.

4. The patient should remain in a seated position breathing in a normal manner for up to 75 minutes, whilst data are collected.
5. The *BreathID[®] MCS* device continuously measures and analyzes the patient's exhaled breath in real time. As the ¹³C-Methacetin is metabolized, the value of the ¹³CO₂/¹²CO₂ ratio in the exhaled breath will change and will be calculated in real time by the *BreathID[®] MCS* device. The device will prompt the operator to enter patient details such as weight and height, age and gender. The *BreathID[®] MCS* device will calculate the *MBT* variables.
6. If at any time the device does not detect patient's breath, or if there is any other deviation from the desired test requirements, the device will produce an appropriate warning signal.
7. At the completion of the procedure, the cannula is removed and the patient is disconnected from the *BreathID[®] MCS* device.

The patient will be under the supervision of the physician or any other qualified medical staff during the entire test.

The operators will be trained how to terminate the breath test early. In the following situations, the *MBT* test will be terminated and a test termination form will be completed:

1. The patient vomits.
2. The patient is inadvertently disconnected.
3. The *BreathID[®] MCS* device malfunctions (In this case, the operator will complete a technical complaint form in addition to the test termination form and contact Exalenz immediately for further instructions)

In all these cases, the next *MBT* cannot be repeated the same day. An entry will be made in the drug/kit accountability log and the bottles will be kept for inspection by the study monitor.

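### Section 16.6 exempts four types of non-fatal SAE from expedited notification whatever their cause, leaving serious cases caused by the breath test, or line bleeds from a US study HVPG, without a timed route to the sponsor

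*Combined protocol and SAP*

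**What the plan says.** Section 16.5 sets the general rule: "The investigator must report any serious adverse event to the sponsor immediately, within 24 hours of awareness, via email". It adds that SAEs meeting the UADE or SUSAR definition go to the authorities by expedited means.

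Section 16.6 makes the exception: "The following situations and non-fatal toxicities that fulfill the definition of an SAE are excluded from expedited notification on an SAE form". The four listed items are a rise in bilirubin, "Elevation liver enzymes", "Nausea, vomiting , diarrhea" and "Bleeding following line insertion". They go instead to the follow-up section of the CRF. The section explains that they are expected from the disease, promises a periodic analysis, and moves to expedited reporting only if the rate proves higher than expected for the stage or severity of disease.

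Other places bear on this:

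- Appendix III: "In rare cases the administration of fluids may cause vomiting".
- Section 13.4: HVPG involves placing a venous introducer, its complications are to be reported as anticipated adverse events, and "in US centers the HVPGs is considered an investigational procedure".
- Section 11.5: the study is discontinued if two or more "patients on Methacetin develop the same CTCAE Grade 3 event", or if one patient has an event of Grade 4 or higher that the breath test caused.

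**The concern.** The exemption is defined by type of event alone. Its justification is about cause: these are things that cirrhosis does to patients. Where the two part company, the wording of the exemption governs what the site does, and a serious harm from a study procedure is filed as if it were background disease. The sponsor may then learn late of the cases that a safety rule with a threshold of one or two patients is meant to catch.

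**Working it through.** No figure in the plan is in dispute, so the check sets the sections side by side.

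**1. Is there any condition on cause in 16.6?** The sentence limits the exemption to non-fatal events on the list. It has no limit on relatedness, grade or severity. The remark that the events come with the disease follows the list as an explanation and is not worded as a condition. Section 13.1, item 10, points to 16.6 as the place that separates reportable from non-reportable SAEs, so a site would apply the list as it stands.

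**2. Does the stated reason cover the listed items?**

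- Bleeding after line insertion: no. It is procedural by its own wording, and line insertion is a step of HVPG (13.4). Section 5.4 names neck or groin hematoma as the most common HVPG complication.
- Vomiting: not always. Appendix III names the test fluid as a possible cause.
- Bilirubin and liver enzymes: the disease explanation is plausible, and the documents report no substrate-related events (8.2.1).

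**3. Which route to the sponsor remains for a listed, non-fatal, related SAE?**

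| Route | Section | Deadline |
|---|---|---|
| SAE report to sponsor | 16.5 | 24 hours, but displaced by 16.6 |
| UADE/SUSAR reporting | 16.5 | Expedited, but to the authorities |
| CRF follow-up section | 16.6 | None stated |
| Test termination form and accountability log (vomiting) | Appendix III | None stated |
| Withdrawal after a Grade 3 or higher event, documented | 11.5, 11.6 | None stated |
| Periodic analysis | 16.6 | No interval, reference rate or threshold |

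The only timed route to the sponsor is the one that 16.6 removes.

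**4. Does the UADE/SUSAR sentence restore it?** Reporting to regulators is the sponsor's task, and the sponsor can act only once it knows of the case. The definition in 16.2 also needs a relation to the investigational product and an unexpected nature or severity. A line bleed fails the first test, because 16.3 rates relatedness only to device or substrate. Vomiting may fail the second: 10.2 expects no breath-test events, yet Appendix III calls vomiting after the fluid expected.

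**5. What does this do to the stopping rule?** The counts in 11.5 are two patients (same Grade 3 event) and one patient (Grade 4 or higher, caused by the breath test). Counts that small need prompt case-level information. A periodic comparison of aggregate rates, judged against what the disease would produce, is not built to detect a first or second case. The effect is confined to events that are also serious: under 16.4 severe and serious are different things, and a Grade 3 event that is not an SAE had no 24-hour route in the first place.

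**The case against.** The strongest reply has four parts.

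- **The events are not lost.** They enter an electronic CRF. Vomiting during the test stops it and triggers a termination form, an accountability entry and retained bottles. Events of Grade 3 or higher generally lead to a documented withdrawal. This stands, and it is why the fault is delay and not loss. None of these channels has a deadline.
- **16.5 may be meant to prevail.** The SUSAR waiver that opens 16.6 covers only complications of disease progression, and a serious, substrate-related liver test rise could meet the SUSAR definition. It can also be argued that expedited notification in 16.6 means notification to authorities. Both readings are possible. But 16.6 instructs the site to use the CRF in place of the SAE form, and no sentence says which section takes precedence.
- **HVPG handling is disclosed.** Section 13.4 names the breath test as the test procedure and HVPG complications as anticipated events. Most patients are European, and there HVPG must be clinically indicated. This stands, and it confines the HVPG part of the point to US centers, where patients enter as consented for HVPG.
- **The liver-test items are weak ground.** One 75 mg dose is given, the metabolite is in routine use at much higher doses, no substrate-related events are reported, and the visit schedule lists no blood draw after the test. This stands too.

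Three stronger readings are tempting and should not be drawn. A reader might infer that every serious HVPG harm in a US patient escapes prompt reporting. It does not: fatal events and unlisted harms such as fistula or dysrhythmia keep the 24-hour rule. A reader might multiply the 2.3% HVPG complication rate in 5.4 by 200 patients and count 4.6 affected cases. That rate is one center's figure for complications of all kinds, the serious bleeding share is not given, and most of the 200 would not be US patients. A reader might also treat liver test rises as an evident substrate signal now hidden; the documents give no support for that.

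**Conclusion.** The point holds in a limited form. As written, a non-fatal SAE of a listed type that the breath test caused, or a serious line bleed from an HVPG done for the study in a US center, has no timed route to the sponsor. For breath-test events this weakens the 11.5 stopping rule. A line bleed cannot trigger the Grade 4 limb of that rule, and whether it counts towards the Grade 3 limb depends on whether the words on breath-test causation govern both limbs, which the text leaves open.

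The size is four event types, non-fatal cases only. The number of patients affected cannot be derived: the documents give neither the serious share of these events nor the number of US patients. The conclusion assumes that sites follow 16.6 literally and that no separate safety plan sets deadlines for the CRF or termination form. It is a fault in wording with a consequence for patient safety, and it should be corrected.

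**What to change.** - In 16.6, limit the exemption to listed events that the investigator judges unrelated to the breath test and to an HVPG done for the study. Send all others through 16.5.
- State that 16.5 takes precedence for any event meeting the UADE or SUSAR definition.
- In 16.3 and the CRF, record relatedness to HVPG, so that the limit can be applied.
- Reconcile 13.4 with this. It says both that HVPG is done for clinical cause and that it is investigational in US centers, and sites need to know which procedures count as done for the study.

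The cost is wording in 16.3 and 16.6 with a clarifying sentence in 13.4, one CRF option, and a few more 24-hour reports. If the sponsor meant to exempt disease-caused events only, the change states that intention.

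No change to the stopping criteria themselves is proposed.

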17 ACCESS TO SOURCE DATA AND DOCUMENTS

17.1 Availability of Source Data and Documents

The Investigator will permit study-related monitoring, audits, EC review, and regulatory inspections (where appropriate) by providing direct access to source data and other documents (i.e. patients' case sheets, blood test reports, histology reports etc.).

17.2 Patient Confidentiality

The patient's name and personal data will remain confidential and will not be published in any way. All data will be coded and stored in locked offices or on password protected computers.

18 MONITORING AND QUALITY ASSURANCE

Monitoring of this study will be to ensure compliance with GCP, local regulations and scientific integrity and will be managed and oversight retained by Exalenz Bioscience (the Sponsor) or its assigned representative.

18.1 Data Collection and Monitoring

An eCRF will be completed for each patient. The EDC (electronic data capture) system will be 21 CFR Part 11 compliant and the site staff and all involved parties will be trained on the system prior to patient enrolment.

IRB and EC members and regulatory authorities will be permitted to review study documents at the site according to local and federal regulations.

19 PUBLICATION POLICY AND FINANCE

It is intended that the results of the study will be reported and disseminated at international conferences and in peer-reviewed scientific journals. The policy regarding publications appears in the non-disclosure agreement signed by each study participant prior to signing of the contract.

Exalenz Bioscience Ltd.	Last update on: Nov 21, 2016
Study Title: Clinical Study of the BreathID[®] MCS System to train the algorithm for the ¹³C-Methacetin Breath Test (MBT) in assessment of Portal Hypertension in Patients with Compensated Liver Cirrhosis	Protocol No.: CSPH-EX-0414 Version: 1.5
Document N^o: CSD00076	Page 52 of 72

20 FINANCIAL ASPECTS

The device and compound will be provided by the Sponsor. Funding for regulatory approvals and administration will also be provided by the Sponsor. Funding will also be provided for a study support staff at local sites.

21 STUDY TERMINATION

The study may be terminated after appropriate consultation between the study sponsor and the chief investigator and co investigators. Conditions warranting termination include, but are not limited to:

- Failure of the investigator to enroll patients at an acceptable rate
- Insufficient adherence to protocol requirements
- Failure to adhere to GCP
- Decision by the study sponsor to suspend or discontinue development of the device or kit

Exalenz Bioscience Ltd.	Last update on: Nov 21, 2016
Study Title: Clinical Study of the BreathID[®] MCS System to train the algorithm for the ¹³C-Methacetin Breath Test (MBT) in assessment of Portal Hypertension in Patients with Compensated Liver Cirrhosis	Protocol No.: CSPH-EX-0414 Version: 1.5
Document N^o: CSD00076	Page 53 of 72

APPENDIX II – DETAILED HVPG PROCEDURE

HVPG procedure: Instruction for a correct measurement

[name], PhD, FRCP

Professor of Medicine, Hospital Clinic-IDIBAPS, University of Barcelona

Abbreviations:

HVPG : hepatic venous pressure gradient

WHVP: wedged hepatic vein pressure

FHVP: free hepatic vein pressure

IVCP : inferior vena cava pressure

RAP: right atrial pressure

Exalenz Bioscience Ltd.	Last update on: Nov 21, 2016
Study Title: Clinical Study of the BreathID[®] MCS System to train the algorithm for the ¹³C-Methacetin Breath Test (MBT) in assessment of Portal Hypertension in Patients with Compensated Liver Cirrhosis	Protocol No.: CSPH-EX-0414 Version: 1.5
Document N^o: CSD00076	Page 62 of 72

HVPG: What is it?

HVPG stand for hepatic vein pressure gradient, which is calculated as the difference between the “wedged” and the “free” hepatic vein pressure (**Figure 1**).

[figure not shown]

Figure 1. *Typical measurement of the hepatic venous pressure gradient (HVPG) with a balloon catheter.* With the balloon deflated, the “free” pressure (FHVP) is recorded. After occluding the hepatic vein by inflating the balloon (*arrows*), the “wedged” pressure (WHVP) is recorded. Between measurements the “zero” pressure is verified by opening the transducer to air. HVPG is calculated as the difference between WHVP (32 mmHg) and FHVP (8 mmHg); in this case it was very high, of 24 mmHg. Note that the two measurements shown in the figure are identical, and that in this patient it took about 45 seconds for WHVP to reach a stable plateau after inflating the balloon.

The wedged hepatic vein pressure is obtained by occluding the lumen of the hepatic vein by inflating a balloon at the tip of the catheter (or by advancing an end-hole catheter as far as it could go into the hepatic vein, a technique that is no longer used as it is less accurate and has more variability than the balloon catheter technique). Once the hepatic vein has been occluded, the static column of blood makes that the pressure sensed by the catheter corresponds to that existing in the hepatic sinusoids. Because of that, the wedged pressure reflects the hepatic sinusoidal pressure. In the normal liver, the hepatic sinusoids are a very uniformly communicated vascular bed. By contrast, in advanced liver disease, especially in cirrhosis, fibrosis and nodule formation makes that the intersinusoidal communications are lost, which makes that when the hepatic vein is occluded, the static column of blood extends beyond the sinusoids and thus reflects portal pressure (**Figure 2**). It has long been known that in different forms of cirrhosis measurement of WHVP equals to the direct measurement of portal pressure, which is much more invasive as requires the transhepatic or surgical catheterization of the portal vein.

Exalenz Bioscience Ltd.	Last update on: Nov 21, 2016
Study Title: Clinical Study of the BreathID[®] MCS System to train the algorithm for the ¹³C-Methacetin Breath Test (MBT) in assessment of Portal Hypertension in Patients with Compensated Liver Cirrhosis	Protocol No.: CSPH-EX-0414 Version: 1.5
Document N°: CSD00076	Page 63 of 72

[figure not shown]
[figure not shown]

Figure 2. *Measurement of wedged hepatic venous pressure (WHVP) in the normal and cirrhotic liver. (A) In the normal liver, after occlusion of blood flow in a hepatic vein with a balloon catheter, the pressure of the static column of blood (WHVP) equilibrates through the interconnected sinusoids. Therefore WHVP is a measurement of the hepatic sinusoidal pressure, which is slightly lower than portal pressure (-1 mmHg). (B) In the cirrhotic liver, the pressure of the static column of blood created by balloon inflation cannot be decompressed at the sinusoidal level due to the sinusoidal narrowing and disruption of the normal intersinusoidal architecture by fibrosis and nodule formation. Because of this, WHVP equilibrates with portal pressure.*

The “free” hepatic vein pressure is obtained by deflating the balloon of the hepatic vein catheter, and is very close to the pressure in the inferior vena cava. If the difference between the free and the IVC pressure is ≥ 2 mmHg it usually reflects that the catheter is advanced too much into an irregular hepatic vein. Because of this the free pressure should always be obtained also in a “retired” position, close to the IVC (**Figure 3**, below)

Exalenz Bioscience Ltd.	Last update on: Nov 21, 2016
Study Title: Clinical Study of the BreathID[®] MCS System to train the algorithm for the ¹³C-Methacetin Breath Test (MBT) in assessment of Portal Hypertension in Patients with Compensated Liver Cirrhosis	Protocol No.: CSPH-EX-0414 Version: 1.5
Document N°: CSD00076	Page 64 of 72

- Inferior vena cava pressure should always be recorded to check if FHVP has been measured correctly.
- FHVP should not be over 2mm Hg above IVCP. If greater (stenosis, compression...), use IVCP to calculate HVPG.
- FHVP should be measured close to its opening into the IVC

Figure 3. *Free pressures should be measured in a “retired” position, close to the IVC.*

In hemodynamic terms, absolute pressures have much less meaning than pressure gradients, the difference of pressure between two points in a vascular system. The pressure gradient (ΔP) is mathematically related to blood flow (Q) and to vascular resistance (r) by Ohms law in the equation: $\Delta P = R \times Q$.

Expressing pressures as pressure gradients beyond being physiologically the correct way has the practical advantage of being independent of external influences. For instance the presence of ascites or obesity may increase the intra-abdominal pressure; this will equally increase the portal pressure and the IVC pressure (or its equivalents, the wedged and free hepatic vein pressure) but will not affect the pressure gradient. The same happens when the electronic pressure transducer is placed to low or to high with respect to the recumbent patient; this will make all pressures to be increased or decreased, but will not alter the pressure gradient. An important final point regarding pressure gradients is that this should be obtained between the WHVP and FHVP (or IVC), not with the right atrial pressure! Using the right atrial pressure introduces a systematic error that overestimates the true pressure gradient and it has been shown that doing this detract the prognostic value of the measurement. In short, the right atrial pressure should not be used to assess portal pressure or hepatic hemodynamics.

Exalenz Bioscience Ltd.	Last update on: Nov 21, 2016
Study Title: Clinical Study of the BreathID[®] MCS System to train the algorithm for the ¹³C-Methacetin Breath Test (MBT) in assessment of Portal Hypertension in Patients with Compensated Liver Cirrhosis	Protocol No.: CSPH-EX-0414 Version: 1.5
Document N°: CSD00076	Page 65 of 72

The procedure

Hepatic vein catheterization is a moderately invasive procedure that should be done by well-trained personnel. It is an ambulant procedure, although it is done with a day-hospital admission in most centers (see video “HVPG measurement” in Garcia-Tsao and Bosch, NEJM 2010, also available in You Tube).

[figure not shown]
The patients usually accept to have repeat HVPG measurements over the time, as the procedure is usually very well tolerated. The factor more closely related to a less good tolerance is the duration over 45 minutes (which most frequently reflect lack of expertise or need for associated procedures such as a transjugular liver biopsy). The median duration of the procedure is 25 minutes.

The procedure should be done preferably in the morning, after fasting overnight. This is so since there is a circadian variation of the HVPG that increases during the day and decreases over the night. On this rhythm there is a superimposed postprandial increase of HVPG that lasts 1-2 hours. If a patient is to undergo repeat measurements these should always be done at approximately the same hour.

The favorite access points are either the right internal jugular vein or the right femoral vein. The procedure is done under slight conscious sedation. Deep sedation should be avoided as it results in exaggerated deep breathing that cause artifacts precluding accurate pressure measurements. Direct ultrasonography guidance should be used, as it saves time and reduces the risk of the more common complications (hematomas, local bleeding, or vascular lesions such as arteriovenous fistulae).

After the access vein has been punctured, a guide wire is advanced into the vein allowing the placement of a venous introducer sheath allowing advancing the balloon catheter under fluoroscopic guidance into a hepatic vein. This usually takes less than 5 minutes.

Once the catheter is in the hepatic vein (preferably, the main right hepatic vein) (Figure 2) an adequate occlusion of the hepatic vein should be checked after inflating the balloon by injecting by hand a small amount of iodinated contrast media. This should show the occluded hepatic vein, without reflux of contrast through the occluded vein or through communications with another hepatic vein. If present, these communications prevent an adequate estimation of the portal pressure. This is extremely uncommon in cirrhosis but very frequent in idiopathic portal hypertension or nodular regenerative hyperplasia (**Figure 3**).

Exalenz Bioscience Ltd.	Last update on: Nov 21, 2016
Study Title: Clinical Study of the BreathID[®] MCS System to train the algorithm for the ¹³C-Methacetin Breath Test (MBT) in assessment of Portal Hypertension in Patients with Compensated Liver Cirrhosis	Protocol No.: CSPH-EX-0414 Version: 1.5
Document N°: CSD00076	Page 66 of 72

[figure not shown]

Figure 3. The presence of communicating vessels between different hepatic veins (arrows) prevents an effective occlusion of the vein and precludes a correct measurement of WHVP. This should be checked in every patient. Such communications are very frequent in patients with idiopathic portal hypertension, but very rare in alcoholic, viral or metabolic cirrhosis.

After documenting the correct occlusion of the hepatic vein, the balloon is released and the catheter is thoroughly rinsed with saline or 5% dextrose and connected to a multichannel pressure recorder for the measurement of the wedged and free hepatic venous pressures (see next section).

Pressure measurements

Correct measurement of intravascular pressures requires fulfilling a series of steps and to have adequate equipment. This is available almost in all hospitals, but not all monitors in IR rooms are adequate for accurate measurements of HVP.

1. Pressure recorder: The adequate pressure recorder should have the following capabilities:

- a) Adjusting the pressure scale for a relatively low range 1-40 or 1-50 mmHg. The pressure scale should be printed together with the pressure tracings, and preferably a milimetric grid should also be disclosed.
- b) Adjusting the recording speed to low velocity (1-6 mm/second).
- c) Capacity of obtaining permanent pressure tracings, either using an on-line printing device, or by generating a printed report from the digitally stored data after completing the procedure.

If the monitor you have is not able of doing this, your center does not qualify for the study.

In addition, a non-invasive monitor for EKG, BP and O2 saturation should be used.

Exalenz Bioscience Ltd.	Last update on: Nov 21, 2016
Study Title: Clinical Study of the BreathID[®] MCS System to train the algorithm for the ¹³C-Methacetin Breath Test (MBT) in assessment of Portal Hypertension in Patients with Compensated Liver Cirrhosis	Protocol No.: CSPH-EX-0414 Version: 1.5
Document N^o: CSD00076	Page 67 of 72

2. Pressure transducer: Nowadays most centers use disposable pre-calibrated transducers that are very reliable.

If you are using another type of transducer or you have doubts on its correct functioning, the transducer should be calibrated against a know pressure. This is done by connecting the transducer to a column of saline of 544 mm height (where it should read 40 mmHg); 272 mm height (where is should read 20 mmHg), and then to 136 mm (where it should read 10 mmHg).

The pressure transducer should be placed in a fixed position that should be set at the mid-axillary line of the recumbent patient. This is the conventional level for the right atrium. Neither the transducer nor the patient should move during the procedure.

3. Balloon catheter: These should have a small (8 – 11 mm inflated balloon diameter), preferably not entirely distal (**Figure 4**).

[figure not shown]

Figure 4. Balloon catheters suitable for HVPG measurements. The balloon is of 8-11 mm in diameter and is not totally distal, so a fully inflated balloon will not occlude the central lumen that will be centered in the axis of the vein.

4. Obtaining the wedged (occluded) hepatic vein pressure (WHVP): After having verified that the catheter is at an adequate position, the hepatic vein is occluded by inflating the balloon while continuously recording the pressure. The hepatic vein pressure will rapidly increase from the free pressure until it finally stabilizes at the final WHVP. This requires usually some 45-60 seconds but sometimes it requires longer periods (**Figures 1 and 5**). The pressure measurement should be continuously recorded for at least 60 seconds (longer if the pressure is still increasing). Because it needs such a long time it is mandatory to run the recorder at very low speed, if not one cannot notice if the

Exalenz Bioscience Ltd.	Last update on: Nov 21, 2016
Study Title: Clinical Study of the BreathID[®] MCS System to train the algorithm for the ¹³C-Methacetin Breath Test (MBT) in assessment of Portal Hypertension in Patients with Compensated Liver Cirrhosis	Protocol No.: CSPH-EX-0414 Version: 1.5
Document N^o: CSD00076	Page 68 of 72

pressure is still increasing or has achieved a plateau. For adequate pressure measurements the patient should be relaxed, asked not to move or talk, and to breathe smoothly.

[figure not shown]

Figure 5. Typical HVPG tracing

Most recorders will allow printing either (or both) the “phasic” oscillating pressure or the “mean” electronically averaged pressure (Figure 6). If possible, both should be recorded. “Mean” pressures are easier to read, but are slow reacting and therefore less adequate to recognize artifacts.

The WHVP should be recorded by triplicate. This allows averaging the values to get a more robust measurement.

Exalenz Bioscience Ltd.	Last update on: Nov 21, 2016
Study Title: Clinical Study of the BreathID[®] MCS System to train the algorithm for the ¹³C-Methacetin Breath Test (MBT) in assessment of Portal Hypertension in Patients with Compensated Liver Cirrhosis	Protocol No.: CSPH-EX-0414 Version: 1.5
Document N°: CSD00076	Page 69 of 72

[figure not shown]

Figure 6. Oscillating and “mean” pressures recorded simultaneously

5. Obtaining the free hepatic vein pressure (FHVP) and the inferior vena cava (IVC) pressure. After completing the measurement of WHVP the catheter should be rinsed, the zero level checked by opening the transducer to atmospheric pressure, and then the FHVP is recorded while the patient is quiet and breathing smoothly. The recording should be run for 20 - 30 seconds.

After obtaining the FHVP the catheter should be slightly withdrawn to obtain another **FHVP at a “retired” position**, with the catheter tip 2-3 cm from the IVC, and from here withdrawn to the **IVC** where pressures are measured again (at the level of the hepatic veins), and finally into the **right atrium**, to measure RAP.

Again, remember that all pressures should be measured by triplicate.

Frequent mistakes

The most frequent mistakes in the measurement of HVPG are due to the fact that the measurement is done at a IR department forgetting to discuss with the radiologist that the main aim of the procedure is to obtain reliable, accurate measurements, with a precision of 0.5 mmHg. The more frequent mistakes are listed and illustrated below:

- a) Inadequate scale: many monitors are pre-calibrated for measuring arterial blood pressure. This scale (usually 0 – 150/200 mmHg) is not adequate for measuring HVPG as the deflections would be too small to allow enough accuracy. The preferred scale should be one in which 1 mmHg equals one division of the grid. Figure n shows an example of a correct and of an incorrect measurement.

Exalenz Bioscience Ltd.	Last update on: Nov 21, 2016
Study Title: Clinical Study of the BreathID[®] MCS System to train the algorithm for the ¹³C-Methacetin Breath Test (MBT) in assessment of Portal Hypertension in Patients with Compensated Liver Cirrhosis	Protocol No.: CSPH-EX-0414 Version: 1.5
Document N^o: CSD00076	Page 70 of 72

- b) Inadequate speed: it is common to run the recorder at a speed of 25-50 mm/sec. This is adequate for EKG but not for HVPG, as a full study would require strips of about 15 foot length, or show only a few seconds of recording.
- c) Inadequate length: a variant of the previous mistake is to run the recording at correct speed but for a too short period, not allowing the pressure to stabilize. This results in underestimation of the true HVPG.
- d) Artifacts due to deep respiration are very common if the patient is excessively sedated and almost invariable when using IV fentanyl. Typically this results in a wide variation of all venous pressures during the respiratory cycle, precluding accurate measurements of HVPG (-, Figure). The patient moving, talking or coughing during the measurements may also cause artifacts. Whenever an artifact occurs, this should be annotated in the tracing and the pressure measurement discarded and repeated.

[figure not shown]

Figure 6. Marked respiratory oscillation due to excessive sedation

Sending the tracings of a HVPG measurement to the central reader.

The original tracings are important source documents that should be kept in the patient's charts. Please, do not send original materials by mail or courier. It is safer, quicker and cheaper to send by e-mail a scanned copy of the tracings as a PDF file.

Each tracing should be clearly identified with the name/code number of the local Principal Investigator (PI); patient's code number and initials, and date.

The tracings should include the calibration used, and 3 sets of measurements of the WHVP (balloon occluded), FHVP, "retired" FHVP, IVC and RAP. Remember to set the recorder at a low speed (1-6 mm/sec), an adequate scale (0-40 or 0-50 mmHg), and to run the measurements at least for 20 seconds for FHVP, IVC and RAP and at least for 60 seconds for WHVP.

Exalenz Bioscience Ltd.	Last update on: Nov 21, 2016
Study Title: Clinical Study of the BreathID[®] MCS System to train the algorithm for the ¹³C-Methacetin Breath Test (MBT) in assessment of Portal Hypertension in Patients with Compensated Liver Cirrhosis	Protocol No.: CSPH-EX-0414 Version: 1.5
Document N^o: CSD00076	Page 71 of 72

